**Title: Effect of Sport Education in University Required PE on Students'
Perceived Physical Literacy and Physical Activity Level**

NCT number: NCT03888885

Date: 12/9/2021

Study Protocol

Research design

This study employed a 10-lesson cluster-randomized study design to examine the effect of sport education on domains of student PL and physical activity levels. Questionnaires, accelerometers, and video recordings of PE lessons were used to collect self-report and objective data measures.

[figure not shown]
Eligibility and randomization

Only one university in Hong Kong fully funded by the University Grants Committee and requires the completion of two semesters of PE coursework for graduation. Lecturers in the PE program are required to have a master's degree or above and have more than 5 years of teaching experience. All lecturers attended a 12-h continuous professional development workshop on sport education. Of the 25 lecturers who attended the workshop, 11 of them consented to participate in the study. The required sample size of students was calculated based on the hypothesized effect sizes and the likely rates of participants dropout for outcome measures. A total number of 2886 students were admitted to the university in the academic year, with an estimated required cluster sample size of 341 with an effect size of 0.25, α of 0.05, and a power of 0.95 (Faul et al. 2007). In anticipation of 10–20% of the dropout rate across data collection phases, this led to a required number of 8 classes for each of the sport education and traditional groups. PE classes were initially grouped by lecturers and types of sports (individual sports, team sports, and physical conditioning) and then randomly assigned to each intervention (Fig. 1) by a computer-generated sequence (GraphPad Software, Inc.) conducted by a statistician who was blind to the purposes of the study. The demographic background and corresponding courses for each of the eight lecturers are shown in Table 1. Students were eligible to participate in the study if they were aged 18 or above and indicated all negative statements in the self-screening Physical Activity Readiness Questionnaire (Thomas et al. 1992) which can uncover heart, circulatory, balance, medication, emotional, and joint problems that could make exercise difficult or dangerous for some people. Written consent for study participation was also obtained.

PE curriculum intervention

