Physical activity measures The globally standardized and validated short version of the International Physical Activity Questionnaire was used to measure self-report physical activity levels (Craig et al. 2003; Hallal et al. 2012). Four generic items of vigorous, moderate, walking, and sitting were included to obtain the physical activity levels from the participants. Example item included the following: During the last 7 days, on how many days did you do vigorous physical activity like heavy lifting, digging, aerobics, or fast cycling (vigorous)? The total

duration of different intensities of physical activity which occurred for at least 10 uninterrupted minutes in the last 7 days was used for calculations (Booth 2000).

Accelerometers (Actigraph wGT3X+) were used to measure the objective physical activity levels (light, moderate, and vigorous) of participants, and physical activity intensity was calculated as a metabolic value (Evenson et al. 2008). The dynamic range of accelerometers is \pm 6MET with 3 axes and 3 mg/LSB of sensitivity. Only data that recorded more than 8 h per day and 5 days per week were used for analysis.

SOFIT is a validated and reliable momentary time sampling and interval observation instrument to gather quantitative data for assessing physical activity during PE lessons (McKenzie et al. 1992). SOFIT includes three intensities of students' physical activity levels (lying down, sitting, standing, walking, vigorous), lesson context (general, knowledge, fitness, skill practice, game play, free time), and teacher behavior (promotes fitness, demonstrates fitness, instructs generally, manages, observes, or other task) or teacher interactions (promoting "in-class" or "out-of-class" physical activity). Each category is coded using interval coding every 20 s (10 s observe; 10 s record) throughout the lesson. The observer decides on what is occurring at the moment an observation interval ends.

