**Title: Effect of Sport Education in University Required PE on Students'
Perceived Physical Literacy and Physical Activity Level**

NCT number: NCT03888885

Date: 12/9/2021

Statistical Analysis Plan

ActiLife 6 software (ActiGraph LLC), a designated software for transferring data from accelerometers to computers, was used to transfer physical activity data with a metabolic cut point of Freedson et al. (1998). IBM SPSS statistics version 22 for Windows (IBM SPSS) was used for all data analysis (Field 2009). One-way analyses of variance (ANOVAs) were used to assess differences between groups in the baseline measures of demographic information, each outcome measure, as well as the mean percentage of physical activity levels, lesson context, and teacher involvement during PE lessons. Pearson's correlation was used to compute the association between self-report and objective physical activity levels. To evaluate the effect of the different types of curriculum interventions on outcome measures, a series of repeated-measures multivariate analysis of variance (MANOVAs) were used with time (baseline, post-intervention, and follow-up) as the within-subjects factor and group (intervention group and control group) as the between-subjects factors. MANOVA analyses are the most appropriate analyses to discern differences between groups over time and to establish any potential group by time interaction effects (Tabachnick and Fidell 2014). Specifically, MANOVA is likely to prevent type I error when dependent outcomes may be correlated and thus potentially share some of the same variances. Post hoc Scheffe analyses were conducted to determine contributing factors to significant MANOVA F values. The significance level was set at 95% for all analyses.

References

Field, A. (2009). *Discovering statistics using SPSS*. London: SAGE Publications Ltd.

Freedson, P. S., Melanson, E., & Sirard, J. (1998). Calibration of the computer science and applications, inc. accelerometer. *Medicine and Science in Sports and Exercise*, 30(5), 777–781.

Tabachnick, B. G., & Fidell, L. S. (2014). *Using multivariate statistics*. Harlow: Pearson Education Limited.

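### Physical activity, a primary outcome, is judged only by an omnibus group-by-time MANOVA, with no named activity variable, wave, signed effect estimate or confidence interval

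*SAP*

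**What the plan says.** The protocol (Data collection protocol) calls self-reported and objective physical activity a primary outcome. It is measured at baseline, at the end of the course (week 11) and at follow-up (week 15). Under Physical activity measures, the questionnaire is described thus: "Four generic items of vigorous, moderate, walking, and sitting were included to obtain the physical activity levels from the participants". The accelerometer gives light, moderate and vigorous activity in a subsample of 64 students per arm.

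The SAP evaluates intervention effects with a series of repeated-measures MANOVAs, with three waves within subjects and two groups between. It gives their purpose as "to discern differences between groups over time and to establish any potential group by time interaction effects". Post hoc Scheffe analyses follow "to determine contributing factors to significant MANOVA F values". One-way ANOVAs are planned for baseline comparisons and in-lesson observation, and a Pearson correlation for agreement between the two activity sources. Neither estimates an intervention effect on weekly activity. The SAP does not say which variables enter which MANOVA, and it names no primary activity variable, wave, contrast, effect estimate or confidence interval.

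The sample-size text (Eligibility and randomization) gives "an estimated required cluster sample size of 341 with an effect size of 0.25", with "α of 0.05, and a power of 0.95". It does not tie the 0.25 to an outcome, a test or an effect-size metric.

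**The concern.** Readers will want to know whether students taught by sport education were more or less active than the others, by how much, and when. An omnibus group-by-time F answers a different question: whether the two groups' profiles over variables and waves differ in any way. More sitting or less vigorous activity contributes to it just as more activity does.

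The follow-up step does not close the gap. It is described only for significant F values and fixes no variable, wave or direction. As a procedure for comparing groups, Scheffe has only one pair here, which the group factor already compares. If the F is significant, the choice of which change to report is made after seeing the data. If it is not, the SAP on its plain reading provides no test of any single activity variable. Either way, no difference in minutes with its uncertainty is planned for a primary outcome.

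**Working it through.** **The plan's figure.** With lambda = f² × N, alpha 0.05, power 0.95 and f = 0.25, a two-group 1-df test needs N = 210. If 0.25 is a standardised mean difference, N = 832. The stated 341 appears if a numerator df of 6 is supplied, but the protocol gives no df and this value was found by search. So 341 does not follow from the stated inputs alone; nor is it shown to be wrong. It is used below only as the sample size.

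**Degrees of freedom (assumed).** df = variables × (3 − 1) wave contrasts × (2 − 1) groups. Four questionnaire variables give 8, three accelerometer intensities give 6, and one summed variable gives 2.

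**Direction.** Noncentrality is lambda = (n/2) μ′C⁻¹μ, where n is students per arm, μ holds the standardised group differences in change from baseline, and C is their correlation matrix. Replacing μ by −μ leaves lambda unchanged, so a gain and an equal loss are equally likely to be significant. This holds even for one variable over three waves. An example with N = 341, 3 or 4 variables, common correlation 0 to 0.6 and wave correlation 0.5: one variable up and another down by 0.304 SD at both later waves gives a significant F with probability 0.92 to 1.00.

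**Power.** The documents give no SDs or correlations. Assumptions:
- N = 341, so n = 170.5, with students treated as independent
- 0.25 SD on each affected change contrast at both later waves
- vigorous–moderate correlation 0.4 and wave correlation 0.5
- walking correlated 0.1 with vigorous and 0.2 with moderate
- sitting correlated −0.1 with the other three

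Single contrast on vigorous plus moderate at one wave: the standardised effect is (0.25 + 0.25)/√(2 + 2 × 0.4) = 0.299. Then lambda = 85.25 × 0.299² ≈ 7.61 and power is 0.79. If only vigorous rises, the effect is 0.25/1.673 = 0.149, lambda is 1.90 and power is 0.28.

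| True effect | Omnibus, 8 df | Single contrast, 1 df |
|---|---|---|
| Vigorous and moderate rise | lambda 10.60, power 0.61 | 7.61, 0.79 |
| Only vigorous rises | 8.50, 0.49 | 1.90, 0.28 |
| Both rise, effect halves by week 15 | 7.95, 0.46 | week 15: 1.90, 0.28; week 11: 7.61, 0.79 |
| Both rise, sitting falls 0.25 SD | 16.04, 0.82 | 7.61, 0.79 |

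For the first row, over vigorous–moderate correlations of 0.2 to 0.6 and wave correlations of 0.4 to 0.7, the omnibus has 0.47 to 0.73 and the single contrast 0.73 to 0.84. With other variable sets, lambda = 85.25 × (2 × 0.0625/1.4) × (2/1.5) = 10.15. That gives 0.72 for vigorous and moderate as separate variables (4 df) and 0.82 for their sum over both waves (2 df).

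**If 0.25 is Cohen's f.** For two groups d = 2f = 0.5. In the first row the 8-df omnibus then has power of at least 0.99 over the whole correlation range, as does the single contrast.

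**Accelerometer subsample (N = 128).** At equal noncentrality, a contrast with 80% power (d about 0.50) corresponds to 51% on 6 df. Which test gains still depends on which variables respond and how they correlate. With one of three variables responding at both waves and wave correlation 0.5, the omnibus has 65% at common correlation 0 and 92% at 0.6.

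**The case against.** A reader might infer that the MANOVA costs the trial power, so that a negative result may only reflect its degrees of freedom. The documents do not support this. The SAP never prescribes an 8-df test. The protocol speaks of the total duration of different intensities, which may mean one summed variable, and over two waves that sum does slightly better (0.82) than the single contrast (0.79). The effect-size metric is unstated; the protocol cites G*Power, and under the Cohen's f reading the gap at N = 341 disappears when both intensities rise. The ranking also reverses under ordinary alternatives, as the table shows. That 6 df reproduces 341 does not show what the investigators intended.

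It can also be said that the protocol's aim is to examine an effect, not to show a rise; that two-sided testing is standard; that a two-sided 1-df test also rejects for a decline; and that group means would show direction informally. All of this stands, so non-directional testing is not in itself the fault. A single contrast, however, comes with one signed estimate for one variable at one wave, and the omnibus F does not. The SAP's own justification, control of type I error with correlated outcomes, does not address this.

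Finally, the SAP does not expressly forbid univariate results after a non-significant F, nor call the MANOVA the deciding test. Both are readings. The second is fair, because no other test of effect on the three-wave activity outcomes is planned.

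**Conclusion.** The concern holds as a gap in specification and estimation. The SAP's only test of effect on repeated activity measures cannot say which variable, wave or direction changed. Its follow-up step does not supply this, and no signed estimate or confidence interval is planned for a primary outcome. This conclusion needs no numerical assumption and holds whichever variables enter each MANOVA.

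A general loss of power is not established. The differences run from 0.18 against the omnibus (0.61 v 0.79) to 0.21 in its favour (0.49 v 0.28), depending on which activities respond. These figures rest on an assumed df, assumed correlations, 0.25 read as SD units of change, and independent students although classes were randomised. They compare two tests and do not describe this trial's actual power.

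**What to change.** For each activity instrument, prespecify the between-arm difference in weekly moderate-plus-vigorous minutes. Name one wave as primary, which is for the investigators to choose, and report the other alongside. Give each difference with a 95% CI in minutes, and test the primary contrast whether or not the MANOVA is significant. List the dependent variables of each MANOVA and keep it as a supportive analysis of the activity profile.

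This changes SAP wording and needs no new data. The price is that the primary contrast is less sensitive to an effect confined to one intensity, to walking or sitting, or to the non-primary wave. The supportive MANOVA covers these.

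### The SAP does not say whether the group F or the group-by-time F decides if the curriculum worked, and the group F gives the pre-intervention wave one third of the weight

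*SAP*

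**What the plan says.** All of this stands in the single text section of the SAP.

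- Purpose of the models: "To evaluate the effect of the different types of curriculum interventions on outcome measures".
- Method: several repeated-measures MANOVAs, each fitted "with time (baseline, post-intervention, and follow-up) as the within-subjects factor and group (intervention group and control group) as the between-subjects factors". Baseline is thus an outcome level, not a covariate.
- Justification: MANOVA is chosen "to discern differences between groups over time and to establish any potential group by time interaction effects". No ranking of the two aims is given.
- Follow-up: "Post hoc Scheffe analyses were conducted to determine contributing factors to significant MANOVA F values". The sentence is not limited to the interaction.
- Level: "The significance level was set at 95% for all analyses", read here as 5% for each test, with no split between tests.

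Baseline measures are compared between groups by one-way ANOVA, but no action is described if they differ. The protocol (Data collection protocol) places baseline in week 1 of the semester, the post-intervention wave at lesson 10 in week 11, and follow-up in week 15. It names no deciding test either.

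**The concern.** Each such model returns a group F, a time F and a group-by-time F. The time F does not compare the arms. The other two do, and they answer different questions. The group F asks whether the arms differ on average over all three waves, one of which precedes the intervention. The group-by-time F asks whether the arms change differently.

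With no deciding test named, two things are at stake. First, a positive finding can arrive by two routes, each at 5%, before any multiplicity over outcomes. Second, the routes can disagree. A difference already present in week 1 that simply persists pushes the group F towards significance and leaves the interaction alone. A baseline gap in the opposite direction can hide a real effect from the group F.

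**Working it through.** **Inputs from the documents.** Three waves, two groups, 5% per test (SAP). Total 341 students, effect size 0.25, power 0.95, 8 classes per group (protocol, Eligibility and randomization). 341/2 gives about 170 per arm.

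**Assumptions, not in the documents.** One outcome, SD 1, equal correlation ρ between waves (0.3 to 0.7), the same effect at both later waves, independent students unless stated. The protocol does not give the scale of its effect size; I use 0.25 SD as an illustration.

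**Does the planned sample size reveal the deciding test?** No. Reading 0.25 as Cohen's f with power 0.95, a between-group test over three waves needs 72 to 169 students in total (ρ from 0 to 0.7) and the interaction needs 27 to 84. Exactly 341 appears with six numerator degrees of freedom, which the protocol does not state. So 341 serves here only to set the scale.

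**1. Two routes.** With equal between-wave correlation, the three-wave mean and the changes from baseline are uncorrelated, so the two tests are close to independent:

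1 − 0.95² = 0.0975, which is 0.0975/0.05 = 1.95 times the stated level.

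Simulation (4,000 trials per setting) gives 9.2% to 10.2%. Whatever the correlation structure, two 5% tests cannot together exceed 10%.

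**2. What the group F estimates.** It is the average of the arm differences at the three waves. With effect δ at the two later waves and gap b carried through all three:

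(b + (b + δ) + (b + δ))/3 = b + 2δ/3.

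For δ = 0.25 and b = 0 this is 0.167 SD.

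**3. Power at δ = 0.25, b = 0, 170 per arm.**

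- Group F: the variance of a student's three-wave mean is (1 + 2ρ)/3. At ρ = 0.5 it is 0.667, the standard error is √(2 × 0.667/170) = 0.0886, and the ratio is 0.167/0.0886 = 1.88.
- Interaction: noncentrality (170/2) × δ² × 2/(3(1 − ρ)). At ρ = 0.5 it is 85 × 0.0625 × 1.333 = 7.08, on 2 and 337 degrees of freedom.
- Baseline-adjusted contrast on the mean of the two later waves: residual variance (1 + ρ)/2 − ρ². At ρ = 0.5 it is 0.50, the standard error is √(2 × 0.50/170) = 0.0767, and the ratio is 0.25/0.0767 = 3.26.

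| ρ | Group F | Group-by-time F | Baseline-adjusted contrast |
|---|---|---|---|
| 0.3 | 55% | 50% | 87% |
| 0.5 | 47% | 66% | 90% |
| 0.7 | 40% | 87% | 97% |

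Simulation agrees for the first two columns: 46–47% and 65–66% at ρ = 0.5.

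**4. A baseline gap, in either direction.**

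- No effect, gap of 0.1 / 0.2 / 0.3 SD carried through: the group F is significant in about 18–19% / 52–62% / 86–91% of simulated trials (ρ = 0.7 to 0.5). The interaction stays near 5%.
- Effect of 0.25 SD, gap of −0.15 SD: the group contrast averages −0.15 + 0.167 = 0.017 SD and the group F rejects in about 5%. The interaction still rejects in 66–87%.

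These rates are conditional on a gap of that size being present.

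**The case against.** **The SAP may intend only the interaction.** It never mentions a group main effect. Its two phrases can be read as one aim, and the only effect it names is group by time. A two-level factor also leaves Scheffé tests nothing to separate between groups, so the post hoc sentence may be about which outcomes or waves drive a result. This reading is possible. But the interaction is listed as a second aim, and no F is excluded. A reader might infer that the SAP sets a rule by which either test counts. It does not; it leaves that open by silence.

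**The group F is a valid test.** A reader might infer that it says nothing about the curriculum. That goes too far. Under randomization with independent students it rejects 5% of the time when there is no effect, and chance baseline gaps are already part of that 5%. It is diluted and carries baseline noise; it is not invalid. This stands.

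**A large gap is not shown to be likely.** No document gives one. With independent students and 168 per arm, a gap of at least 0.20 SD has probability of about 7%; at an assumed class intraclass correlation of 0.05, about 19%. Classes were grouped by lecturer and type of sport before assignment, which should limit imbalance, and the baseline ANOVAs would show a gap. This stands, so the conditional rates in step 4 show how the test behaves and are not expected error rates.

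**The interaction is not immune to clustering.** Class differences that are constant over time inflate the group F and spare the interaction. A reader might infer that the interaction is therefore safe. Students take ten lessons in intact classes after baseline, so class effects may develop later. With assumed class-by-wave variance of 0.02 or 0.05 at the two later waves only, simulated false rejection by the interaction is 13–15% or 26%, against 7% or 9% for the group F. This stands: clustering is a separate defect and cannot be used to rank the two tests.

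**Conclusion.** The point holds as a missing decision rule with a measurable cost. As written, the plan leaves room for two 5% routes to a curriculum claim, about 9.75% per outcome if both are used. That figure assumes independent students and equal between-wave correlation, and it matters only if a significant group F would be reported as a curriculum effect, which the SAP neither says nor rules out. The dilution to two thirds and the one-third weight on baseline follow from the model itself; the dilution figure needs only an equal effect at the two later waves. The power figures depend on the assumed correlation, and the group F is slightly ahead of the interaction at 0.3. All magnitudes are for one outcome, because the SAP gives neither the number of MANOVAs nor the outcomes in each.

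**What to change.** Add a rule to the SAP along these lines:

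> The effect of the curriculum is judged only by [one named test]. The group and time main effects are reported descriptively and are not interpreted as evidence of a curriculum effect. Post hoc tests are done only when the named test is significant.

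The named test can be the group-by-time F. Preferably it is one baseline-adjusted group contrast, with the later wave, or the average of the two later waves, fixed in advance. Under the assumptions above, the contrast on the average has more power than either F at every correlation tried.

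**Cost.** The group-by-time option is SAP wording only, with the same data and model. The baseline-adjusted contrast uses the same data with baseline moved to a covariate. The sponsor gives up any claim that rests on the group main effect alone. The interaction test has slightly less power than the group F if between-wave correlation is about 0.3. Because the SAP is written in the past tense, a rule added after results are known should be dated and labelled as such.

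**What it does not do.** The rule does not control error from class clustering, including class effects that develop after baseline. Class must be modelled separately, whichever test is named.

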Participants within the control group classes attended PE classes where teachers used traditional teacher-directed methods to teach the specific activities. These lessons started with a teacher-directed warm-up routine, followed by direct instruction of skills practices, and games without a consistent team and modification to meet the objective of the courses. Within the direct teaching approach, the teacher was assigned responsibility for all task presentation components of the learning tasks. No student role responsibilities or student-directed tasks were included within this approach. Students within the intact class changed teams each lesson and scores were not formally recorded for the game outcomes. Analysis with the sport education benchmark observational instrument revealed none of the instructional behaviors associated with the key features of the model.

Data collection protocol

During the first week of the semester, a baseline questionnaire was distributed by the researchers and lecturers to all participants to obtain students' self-reported information including perceived PL, physical activity levels, and perceptions of motivational climate in PE classes. Demographic information is related to participants' age, gender, ethnicity, undergraduate program and year of study, and years of sport participation. PL is both an antecedent and consequence of physical activity (Edwards et al. 2017) and represents the lived experience of the PL journey of an individual (Sum et al. 2018a). A primary outcome measure was the participants' self-reported and objective physical activity levels. As there may be an over-reporting of the self-report physical activity levels, a subsample of 64 randomly selected student participants per intervention group also collected objective physical activity levels using accelerometers. Accelerometers were worn for at least 8 h per day in seven consecutive days during the first week of the semester. During the intervention, all lessons were videotaped and coded using the System for Observing Fitness Instruction (SOFIT) which elicits percentage of PE time at different intensities of physical activity, lesson context, and teacher involvement in PE lessons. Participants recompleted the questionnaire, and the subsample wore the accelerometers during the post-intervention phase (the 10th lesson at 11th week of semester) and the follow-up phase (15th week of semester).

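### Type I error is not controlled across the series of MANOVAs: about 10% for the two primary measures tested separately, and about 13–27% if three to six MANOVAs are run

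*SAP*

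**What the plan says.** The SAP has a single section. For the effect of the curriculum it states that "a series of repeated-measures multivariate analysis of variance (MANOVAs) were used with time" as the within-subjects factor (baseline, post-intervention, follow-up) and group as the between-subjects factor. It gives neither the number of MANOVAs nor the outcomes in each, and it names no primary outcome.

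Three sentences bear on error control:

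- On the choice of method: "MANOVA is likely to prevent type I error when dependent outcomes may be correlated".
- On follow-up: "Post hoc Scheffe analyses were conducted to determine contributing factors to significant MANOVA F values".
- On the level: "The significance level was set at 95% for all analyses", which I read as 5% for each analysis.

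The Protocol, under Data collection protocol, adds: "A primary outcome measure was the participants' self-reported and objective physical activity levels". The two measures are not ranked, and no alpha is divided between them. The same section says that "a subsample of 64 randomly selected student participants per intervention group also collected objective physical activity levels using accelerometers". From Physical activity measures onward, the Protocol describes six outcome instruments apart from the lesson observations: the activity questionnaire (IPAQ), the accelerometer, SIMS, PACES, PPLI and EDMCQ-PE.

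**The concern.** A MANOVA gives one overall test for the variables inside it, and Scheffe comparisons apply only once that overall test is significant. Neither limits the chance that at least one of several separate MANOVAs is significant when the curriculum has no effect. The SAP has no alpha split, order of testing or gate across the series.

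Fitting everything in one model is not a practical way out. Accelerometer data are planned for 64 per group, 128 students, against a required sample of 341. A joint complete-case model would set aside 1 − 128/341 ≈ 62% of the questionnaire respondents. The two primary measures therefore need separate models, which means at least two tests.

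At stake is what a significant result means. With no stated success rule and no stated count, a reader who sees one significant MANOVA cannot tell how likely such a finding was by chance. The problem would remain even if every MANOVA were exactly valid, so it is distinct from the handling of class clustering and from the comparisons made within a model.

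**Working it through.** The documents state no family-wise error rate, so there is no figure of the plan's own to reproduce.

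**Inputs**

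- Level per test: 0.05 (SAP).
- Primary measures: 2 (Protocol, Data collection protocol).
- Number of MANOVAs, k: not stated. I take k = 2 for the two primary measures in separate models, k = 3 if scales are pooled, and k = 6 for one MANOVA per instrument. The last two are assumptions.
- Correlation between instruments: not stated. Range taken: 0 to 0.7.
- Each MANOVA is assumed to hold its nominal 5%, and any one significant result is assumed to be claimable.

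**Independent tests.** The chance of at least one false positive is 1 − (1 − 0.05)^k.

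| k | Calculation | Result |
|---|---|---|
| 2 | 1 − 0.95² | 9.75% |
| 3 | 1 − 0.95³ | 14.3% |
| 6 | 1 − 0.95⁶ | 26.5% |

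**Correlated outcomes.** The SAP itself expects the outcomes to be correlated, so this matters. A null simulation used Hotelling's T² on two change contrasts per variable, with 170 per arm (64 for the accelerometer) and 4,000 replicates. Each test alone rejected at about 5%.

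| Between-instrument correlation | Three MANOVAs (IPAQ, accelerometer, PPLI) | Six MANOVAs |
|---|---|---|
| 0 | 14.2% | 26.6% |
| 0.3 | 13.0% | 24.9% |
| 0.5 | 13.5% | 23.6% |
| 0.7 | 13.2% | 22.2% |

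These give the 13–27% range. Small differences between rows are simulation noise.

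A cruder check replaces each MANOVA by a single z-test and correlates the test statistics directly. At correlations of 0.3 to 0.7 it gives 8.3–9.5% for two tests, 11.0–13.6% for three and 16.4–24.2% for six. It overstates the dependence, because multivariate tests with several degrees of freedom are less dependent than single z-tests at the same correlation. Even so, every figure is above 5%.

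**Effect of Holm on power.** With two tests, Holm compares the smaller p-value with 0.05/2 = 0.025 and, if that is met, the larger with 0.05. In the normal approximation:

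- 95% power at 0.05: Φ(1.960 + 1.645 − 2.241) = Φ(1.364) ≈ 91%.
- 80% power at 0.05: Φ(1.960 + 0.842 − 2.241) = Φ(0.561) ≈ 71%.

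**A gate that would not work.** Suppose PPLI were tested at 0.05 after any one primary success, on top of Holm. If one primary effect is real and almost certain to be detected, while the other primary measure and PPLI are null, both nulls are tested at 0.05. The error is then up to 1 − 0.95² = 9.75%, the same inflation as before. Holm has already passed the full 0.05 to the second primary measure, so none is left for PPLI until both succeed.

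**The case against.** Several stronger readings are tempting, and the documents do not support them.

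- **That the SAP claims error control across the whole plan.** A reader might infer this, but the sentence is hedged and concerns dependent outcomes analysed together. The gap is silence about multiplicity between models.
- **That the error rate simply is 14–26%.** The SAP says only that there is a series. If all questionnaire scales shared one model and the accelerometer had another, k would be 2 and the rate 9.75%. The two primary measures alone never give more than about 10%.
- **That success on either primary measure is enough.** No such rule is written. The Protocol brings in the accelerometer because self-report may be inflated, and the SAP correlates the two measures, which also fits a corroborating role. If both had to be significant, the primary claim would not be inflated. The correct criticism is that the rule is unstated.
- **That PPLI belongs below activity.** The trial title puts perceived physical literacy first, and the Protocol speaks of a primary outcome measure with the indefinite article. The ranking is for the sponsor to state.

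A further objection is timing. Both documents are written in the past tense, and the Protocol already reports fidelity results. A hierarchy added now may be post hoc and cannot be presented as prespecified.

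These objections limit the size of the claim and shape the remedy. They do not supply a control across models: for any k of 2 or more at 0.05 each, with any one result claimable, the family-wise rate exceeds 5% unless the tests are perfectly dependent.

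**Conclusion.** The point holds in a conditional form. Error across the MANOVAs is uncontrolled, and the safeguards the SAP offers act only inside one model. The size is about 10% for the two primary measures tested separately, and about 13–27% for three to six MANOVAs.

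The figures rest on three assumptions: each MANOVA holds its nominal 5%, any one significant result may be claimed as an effect, and, for the wider range, the count is three to six. That correlation lowers the rate only slightly is a simulation result for assumed correlations up to 0.7. I am confident of the mechanism and of the figure for two tests; the upper range depends on a count that the plan should have given.

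**What to change.** 1. Limit the type I error sentence in the SAP to outcomes within one MANOVA.
2. List every MANOVA and the outcomes in it, and state the success rule.
3. Test the two primary group-by-time comparisons, self-reported and accelerometer activity, in separate models with Holm at a family level of 0.05. Word any activity claim by the measure that met its threshold.
4. Report the other instruments as secondary or exploratory, with p-values labelled as unadjusted.
5. If the sponsor wants a confirmatory claim for PPLI, either test it at 0.05 only after both primary measures succeed, or include it in the Holm family. With three members, the smallest p-value must then be at most 0.05/3 ≈ 0.0167.
6. Label any choice made after data were seen as post hoc, with its date.

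No new data are needed. The cost is that the smaller primary p-value must be at most 0.025, so a test with 95% power at 0.05 has about 91%, and one with 80% has about 71%. The scales outside the confirmatory family lose confirmatory status. Holm needs no ranking of the two primary measures, which leaves less room for a data-driven choice between them.
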